#### ***4.5 DLT Definition and Escalation Decision Process***

Dose Limiting Toxicities will be defined by toxicity occurring during the first 4 weeks of this study. Any non-hematologic AE of Grade 3 or higher that is judged to be probably treatment-related will be considered a DLT with the exceptions of fatigue; rash attributable to regorafenib; or nausea, vomiting, or diarrhea that has improved to Grade < 1 within 72 hours. Any non-hematologic AE of Grade 4 or higher of any duration that is judged to be probably treatment-related will be considered a DLT except for elevations of lipase and/or amylase in the absence of clinical pancreatitis.

The following hematologic DLT will be considered if any occurs in the first cycle:

- 1) grade 4 neutropenia lasting more than 7 days
- 2) febrile neutropenia (T > 100.4 F in presence of ANC <500)
- 3) platelet count less than 25,000/mm^3
- 4) platelet count less than 50,000/mm^3 with clinically significant hemorrhage

If a DLT is observed in exactly 1 patient in the first cohort of 3, the cohort will be expanded to 6. If a DLT occurs in 2 or more patients per cohort, then the cohort one dose below will be the declared the MTD provided that at least 6 patients have been treated at that level with fewer than one third having DLTs. The rules for dose escalation and cohort size are outlined in Table 3. No intra-patient dose escalation is planned.

***Evaluable Patients:*** Patients will be evaluable for toxicity if they have taken one dose of HCQ and entinostat. Patients who experience a dose-limiting toxicity will be evaluable for the cohort after at least one dose of HCQ and one dose of entinostat. To be considered for evaluability in a Phase I cohort in the absence of dose-limiting toxicity, patients should have completed  $\geq 85\%$  of HCQ doses, and at least 3 of 4 entinostat doses. Phase II patients will be evaluable for response if they have completed 85% of their expected dose of HCQ and at least 3 doses of entinostat in the initial 4 weeks, in the absence of progression. Patients who do not meet these criteria will be replaced. In the unexpected event of excess toxicity at dose level 1, there is provision (Table 3) for a dose reduction of both HCQ and entinostat.

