### 7.1.2 Phase II

Single agent regorafenib showed ORR of 1% in phase III trials in advanced colorectal cancers. We anticipate being able to improve this response rate substantially, perhaps to 15% or more. We will enroll a total 26 patients at the RP2D, including those treated during the phase I portion of the study. Sample size calculations are based on an assumption of at least 20 evaluable patients. With 20 patients, an exact binomial test with a 0.05 one-sided significance level will have 84% power to detect an improvement from the historical rate (null hypothesis proportion) of 1% to an improved rate (alternative proportion) of 15%.

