### 7.3 *Sample Size/Accrual Rate*

Phase I: The phase I study will involve six possible dose levels, although accrual at more than 3 or 4 levels is very unlikely. The total sample size will range from a minimum of 12 to a maximum of 24 patients. We expect accrual to be completed within 6-9 months.

Phase II: During the Phase II portion we will enroll up to 20 additional patients and expect an accrual time of approximately 1 year.

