### ***10.1 Definitions***

Evaluable for toxicity: All patients will be evaluable for toxicity from the time of their first treatment on study.

Evaluable for objective response: Only those patients who have measurable disease present at baseline, have received at least one cycle of therapy, and have had their disease re-evaluated will be considered evaluable for response. These patients will have their response classified according to the definitions stated below. (Note: Patients who exhibit objective disease progression prior to the end of cycle 1 will also be considered evaluable.)

Evaluable Non-Target Disease Response: Patients who have lesions present at baseline that are evaluable but do not meet the definitions of measurable disease, have received at least one cycle of therapy, and have had their disease re-evaluated will be considered evaluable for non-target disease. The response assessment is based on the presence, absence, or unequivocal progression of the lesions.

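### The Phase II response rate has two different evaluability rules (4.5 and 10.1) and no all-treated analysis, so the primary estimate has no single denominator and is likely to be too high.

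*Combined protocol and SAP*

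**What the plan says.** The Phase II primary objective (1.2.1) is to determine the response rate of the combination. Four places bear on its denominator.

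- **7.1.2:** "Sample size calculations are based on an assumption of at least 20 evaluable patients". The planned total is larger: "We will enroll a total 26 patients at the RP2D, including those treated during the phase I portion of the study". The section neither defines evaluable nor points to a definition.
- **4.5, Evaluable Patients:** "Phase II patients will be evaluable for response if they have completed 85% of their expected dose of HCQ" and have taken at least 3 entinostat doses in the first 4 weeks, in the absence of progression. It continues: "Patients who do not meet these criteria will be replaced".
- **10.1:** patients with measurable disease at baseline who "have received at least one cycle of therapy, and have had their disease re-evaluated will be considered evaluable for response". There is no dose threshold and no replacement. A note adds: "Patients who exhibit objective disease progression prior to the end of cycle 1 will also be considered evaluable".
- **7.3:** "During the Phase II portion we will enroll up to 20 additional patients".

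Neither 7.1.2 nor 7.2 plans a response rate in all treated or all enrolled patients. In 10.1, only toxicity is assessed in all patients.

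**The concern.** The two rules select different patients, in both directions. A patient below 85% of HCQ in cycle 1 who is scanned at week 8 counts under 10.1 but not under 4.5. A patient adequately dosed for 4 weeks who then dies, declines or withdraws without a scan counts under 4.5 but not under 10.1. The text does not say whether one rule or both apply.

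Two further gaps widen the uncertainty. The response rule in 4.5 is written for Phase II patients only, although 7.1.2 also counts Phase I patients treated at the RP2D. Section 4.3 replaces patients who leave that cohort before 2 cycles for reasons other than toxicity, such as progression, without saying whether they remain among the 26.

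Both rules condition on what happens after treatment starts. Patients lost through early toxicity, missed doses, withdrawal, or death or decline without a scan are less likely to be responders, so removing or replacing them tends to raise the rate. With so few responders expected, one patient's status can also decide the test.

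**Working it through.** **Inputs.** From 7.1.2: null 1%, alternative 15%, one-sided exact binomial test at 0.05, 20 evaluable, 26 enrolled at the RP2D. The documents give no non-evaluable share. I assume m = 1 to 6 of 26; 6 is the extreme, the gap between 26 enrolled and the sizing floor of 20.

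**1. The plan's own figure.** At n = 20 the smallest rejection count is 2 responders: P(X ≥ 2; 20, 0.01) = 0.0169, whereas P(X ≥ 1; 20, 0.01) = 0.182. Power is P(X ≥ 2; 20, 0.15) = 0.824, against the stated 84%. That is close enough; the power figure is not the problem.

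**2. How easily a patient fails 4.5.** If the expected dose means the planned 28 days (an assumption), 24/28 = 85.7% passes and 23/28 = 82.1% fails. Five held or missed days are enough. Section 5.3.1 requires HCQ to be held for related events of grade 3 or higher.

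**3. Inflation of the estimate.**

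- No non-evaluable patient responds: factor 26/(26 − m), which is 1.04 at m = 1, 1.13 at m = 3 and 1.30 at m = 6.
- Non-evaluable patients respond at half the all-treated rate: factor (26 − 0.5m)/(26 − m), which is 1.02, 1.065 and 1.15 at the same values of m.

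With 3 responders (Clopper-Pearson 95% intervals):

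| Denominator | Rate | 95% CI |
|---|---|---|
| 26 (all treated) | 11.5% | 2.4–30.2% |
| 25 (m = 1) | 12.0% | 2.5–31.2% |
| 20 (m = 6) | 15.0% | 3.2–37.9% |

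The shift can go the other way. If one of the 3 responders is among those excluded, the rate is 2/25 = 8.0% to 2/20 = 10.0%.

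**4. A case where the rules disagree on the test.** Take 26 treated, all scanned, with 2 responders, one of them below 85% of HCQ.

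- 10.1 set: 2/26, P(X ≥ 2; 26, 0.01) = 0.028. Rejects 1%.
- 4.5 set: 1/25, P(X ≥ 1; 25, 0.01) = 1 − 0.99^25 = 0.22. Does not reject. If the dropped responder is replaced by a non-responder, 1/26 gives 0.23.

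**5. Type I error.** Let the true all-treated rate be 1%, with all responders among the evaluable, so the evaluable rate is 0.01 × 26/(26 − m).

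- Without replacement, P(X ≥ 2) with n = 26 − m runs from 0.0277 (m = 1) to 0.0275 (m = 6).
- With replacement until 26 are evaluable, it runs from 0.030 (m = 1) to 0.045 (m = 6). That needs 26 × 26/(26 − m), or about 27 to 34 treated, more than the 26 in 7.1.2.

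It does not exceed 0.05 in either case.

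**The case against.** The strongest reply is that the two rules can be read together: 10.1 states necessary conditions, a cycle is 28 days, and 4.5 only says how much drug counts as a cycle. That would give one denominator. It is a possible reading, but the text never states it, and it excludes the most patients.

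Other points stand in part.

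- **Early progressors are largely kept.** The 10.1 note keeps them. In 4.5 the progression clause most naturally waives the dose threshold, in parallel with the Phase I wording "To be considered for evaluability in a Phase I cohort in the absence of dose-limiting toxicity". Follow-up after stopping (4.6), the Table 12 note on documenting progression, and the 2-week scan window (Appendix A, note 9) also shrink the never-rescanned group.
- **The 85% may be measured against the dose expected after protocol-required holds.** Then held days would not count, and many patients with early toxicity would stay evaluable. The wording allows this, and step 2 would then apply only to missed days.
- **The case in step 4 lowers the estimate and is uncommon.** If each responder has a 10–20% chance of falling below the threshold (an assumption), the chance of exactly 2 responders in 26 with at least one dropped is about 3–5% at a true rate of 15%. The case shows that the result is not uniquely defined; it is not evidence of upward bias.
- **The shift is small beside the sampling error.** Even at the extreme it is 3.5 points (11.5% to 15.0%), inside an interval of 2.4–30.2%.
- **A cross-reference alone would settle which rule applies.** It would, but it would leave a primary estimate conditioned on post-treatment events with no all-treated rate beside it.

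**Conclusion.** The concern holds and should be fixed. The plan has two incompatible evaluability rules, the sample-size section cites neither, and no all-treated rate is planned. Upward bias is likely but not certain, because 4.5 can also drop a responder who missed doses. Its size rests on the assumed 1 to 6 non-evaluable of 26: 1.04- to 1.30-fold if none of them responds, 1.02- to 1.15-fold if they respond at half the all-treated rate. At the extreme, 3 responders would read as 15.0%, the rate that section 2.8 calls promising, instead of 11.5%. The test against 1% remains valid; what suffers is the estimate and the uniqueness of the primary result.

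**What to change.** In 7.1.2, define one primary response population: every patient who took at least one dose of study treatment at the RP2D, including Phase I patients treated at that dose. Count anyone without a documented response as a non-responder. In 4.5, remove the exposure condition and the replacement clause from response evaluability, and align its progression wording with 10.1. Phase I DLT evaluability and the tolerability replacement in 4.3 stay as they are. Report the 10.1 evaluable set as a sensitivity analysis.

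This costs protocol and SAP wording only and needs no additional patients. The downside is a lower point estimate. With 26 treated, the 2-responder rule has alpha 0.028. Power is P(X ≥ 2; 26, 0.15) = 92% if 15% is the all-treated rate. If 15% holds only among 20 of the 26, the all-treated rate is 0.15 × 20/26 = 11.5% and power is 82%, close to the exact 82.4% at n = 20. If replacements under 4.3 take the number dosed above 26, the critical value stays at 2 up to n = 35 (alpha 0.048).

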**Table 4: Phase I: Criteria for Dose Escalation and Cohort Size**

Number of patients with DLT	Rule
0/3 DLT	Escalate
1/3 DLT	Increase cohort to 6 patients
$\geq 2/3$ DLT	De-escalate dose
If the cohort size is increased to 6 patients, the following rules apply	
Number of patients with DLT	Rule
1/6 DLT	Escalate
2/6 DLT	MTD is next lower dose
$\geq 3/6$ DLT	De-escalate dose

The doses of entinostat and HCQ will remain the same for each patient throughout treatment unless there is a need for a dose decrease for toxicity. These DLT decisions are assuming the toxicity is characteristic of entinostat or HCQ.

DLT determination is complex in this three-drug combination, and should the DLT toxicities be more likely associated with regorafenib, a lower dose of regorafenib may be required.

#### ***4.6 Duration of Treatment***

Patients will continue therapy on 28-day cycles until disease progression or the constraints of this therapy are deemed to be detrimental to the patient's health. In this event, the protocol should be discontinued. Furthermore, the protocol will be discontinued should the patient withdraw consent. All patients in whom protocol therapy has been discontinued will be followed for progression of disease and survival.

#### ***4.7 Measurement of Response***

Patients will be assessed on regularly prescribed intervals in order to determine if there is evidence of disease progression. A CT or MRI of the abdomen/pelvis and chest (if thoracic disease is present) will be obtained at 8 and 16 weeks, then every 8-12 weeks per standard practice.

#### ***4.8 Laboratory Testing***

Patients will have laboratory testing at the pre-treatment screening visit, cycle 1 day 1, and cycle 1 day 15 as described in the schedule of events (Appendix A), including complete blood count with differential and comprehensive metabolic panel with magnesium and phosphorous. Complete blood counts will be continued every two weeks until week 8, and then every four weeks if the hematologic toxicity is tolerable. Comprehensive metabolic panel, magnesium, and phosphorous will be checked every 4 weeks after the initial testing unless there is concerning toxicity. CEA will be checked at baseline, and, if it is elevated above the laboratory upper limit of normal, will be checked on day 1 of each 28-day cycle. Prothrombin time (PT) and activated prothromboplastin time (aPTT) will be checked at baseline. Patients on non-prophylactic anticoagulation will have a complete blood count weekly for cycles 1 and 2, and every 2 weeks with subsequent cycles.

For correlative pharmacodynamic testing, blood samples for peripheral blood mononuclear cells (PBMCs) will be obtained on cycle 1 day 1 (prior to therapy administration), cycle 1 day 2, and cycle 1 day 15. As in our previous study, autophagy inhibition will be assessed using western analysis of autophagy markers in PBMCs. HDAC inhibition will be measured through multiparametric flow cytometric analysis of histone and non-histone targets of de-acetylation enzymes in PBMCs in collaboration with [name], NIH. In addition, the effects of the treatment on lymphocyte subsets will be analyzed by flow cytometry. The procedures for this are further described in the laboratory manual.

#### ***4.9 Tumor Biopsy***

All patients receiving treatment on this trial should have available archival tumor tissue for analysis. This tissue should be that which was procured at the time of diagnosis and prior to treatment either through colonoscopic biopsy, surgical excision, or core biopsy of a metastatic site. Formalin-fixed, paraffin-embedded tissue will suffice. About 20 unstained slides, 5 microns thick will be requested. During the phase II portion of the study, additional tumor biopsy samples will be obtained in consenting patients with accessible disease between day 15 and day 22 of cycle 1, as permitted by scheduling of the procedure. In these paired biopsy samples, analysis of antigens including FOXO1

expression, localization, phosphorylation, and acetylation will be performed before and after treatment. Gene expression will also be analyzed in these patients by RNA-Seq and cytokine analysis will be performed in collaboration with Drs [name] and [name] at Salk.

#### ***4.10 Gene Expression Profiling***

For the tumor genomic characterization, we plan to submit all patients' baseline tumor biopsies for NGS analysis in a CLIA-approved test developed in the Department of Pathology at Penn (CPD Solid Tumor Panel, version 2), or equivalent, or more in-depth analysis as funding may permit.

### **5.0 DOSE MODIFICATIONS**

Toxicity will be graded using the NCI Common Toxicity Criteria, CTCAE v. 4.03, which is available on the NCI website [www.ctep.cancer.gov](http://www.ctep.cancer.gov). As specified in the following tables, dose modification should be based upon the worst grade of toxicity experienced. Dose reductions should be continued for subsequent cycles. Exceptions may be made after discussion with the Principal Investigator.

#### ***5.1. Regorafenib***

Interrupt regorafenib for the following:

- NCI CTCAE Version 4.03 grade 2 hand-foot skin reaction (HFSR) [palmar-plantar erythrodysesthesia (PPE)] that is recurrent or does not improve within 7 days despite dose reduction; interrupt therapy for a minimum of 7 days for grade 3 HFSR
- Symptomatic Grade 2 hypertension
- Any NCI CTCAE v4.03 Grade 3 or 4 adverse reaction attributable to regorafenib

Reduce the dose of regorafenib to 120 mg:

- For the first occurrence of Grade 2 HFSR of any duration
- After recovery of any Grade 3 or 4 adverse reaction attributed to regorafenib
- For Grade 3 aspartate aminotransferase (AST)/ alanine aminotransferase (ALT) elevation (see Note below)

Reduce the dose of regorafenib to 80 mg:

- For re-occurrence of Grade 2 HFSR at the 120 mg dose
- After recovery of any Grade 3 or 4 adverse reaction at the 120 mg dose (except hepatotoxicity)

Discontinue regorafenib permanently for the following:

- Failure to tolerate 80 mg dose
- Any occurrence of AST or ALT more than 20 times the upper limit of normal (ULN)  
Grade 4
- Any occurrence of AST or ALT more than 3 times ULN with concurrent bilirubin more than 2 times ULN
- For any of the following complications: gastrointestinal perforation/fistula, hemorrhage (severe or life-threatening), reversible posterior leukoencephalopathy syndrome (RPLS), wound dehiscence

**Note:** With regorafenib, as many as a third of patients may require dose decreases. These can often be temporary and patients can often be re-dosed at starting doses after resolution of toxicity.

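### At regorafenib 120 mg, Section 5.1 lets some grade 3-4 liver events resume at the same dose, while other grade 3-4 reactions step down to 80 mg

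*Combined protocol and SAP*

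**What the plan says.** All the operative rules are in Section 5.1.

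- **Interrupt:** "Any NCI CTCAE v4.03 Grade 3 or 4 adverse reaction attributable to regorafenib". There is no exception for dose or organ.
- **Reduce to 120 mg:** "After recovery of any Grade 3 or 4 adverse reaction attributed to regorafenib", and separately "For Grade 3 aspartate aminotransferase (AST)/ alanine aminotransferase (ALT) elevation (see Note below").
- **Reduce to 80 mg:** recurrent grade 2 hand-foot skin reaction at 120 mg, and "After recovery of any Grade 3 or 4 adverse reaction at the 120 mg dose (except hepatotoxicity").
- **Stop permanently (liver):** "Any occurrence of AST or ALT more than 20 times the upper limit of normal (ULN"), which the bullet labels grade 4, and "Any occurrence of AST or ALT more than 3 times ULN with concurrent bilirubin more than 2 times ULN".
- **Stop permanently (other):** failure to tolerate 80 mg, and a short list of non-liver complications.
- **Note:** the only Note in the section says that "as many as a third of patients may require dose decreases" and that "patients can often be re-dosed at starting doses after resolution of toxicity". It does not mention AST, ALT, bilirubin or the liver.

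Elsewhere, Section 5.0 carries reductions forward to later cycles unless an exception is discussed with the principal investigator. Table 7 lists 160, 120 and 80 mg with no event rules.

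**The concern.** An exception that singles out hepatotoxicity would normally be there to make its management stricter. Here it removes the step down to 80 mg and supplies no stop in its place, which looks like a drafting omission.

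A patient who has just recovered from a grade 3 liver event on 120 mg could be put back on 120 mg by following the text. Following the pointer to the Note could even lead to 160 mg. A patient with a non-liver grade 3 reaction at the same dose would go to 80 mg.

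Liver events are foreseeable in this combination. Table 9 lists raised ALT, AST and bilirubin for entinostat. Section 2.5 reports grade 3-4 liver abnormalities in the regorafenib trial in Asia. Section 3.1.12 admits patients with liver metastases whose AST/ALT is up to 5 x ULN.

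**Working it through.** The plan gives no figure to reproduce on this point. The check applies each Section 5.1 rule to each dose and type of event attributed to regorafenib.

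| Event | On 160 mg | On 120 mg | On 80 mg |
|---|---|---|---|
| Grade 3 AST/ALT, up to 20 x ULN, bilirubin not above 2 x ULN | Interrupt, then 120 mg | Interrupt; 80 mg excepted; no stop rule met | Interrupt, then stop* |
| Isolated grade 3-4 bilirubin, AST/ALT not above 3 x ULN | Interrupt, then 120 mg | Interrupt; 80 mg excepted; no stop rule met | Interrupt, then stop* |
| AST/ALT above 3 x ULN with bilirubin above 2 x ULN | Stop | Stop | Stop |
| AST/ALT above 20 x ULN | Stop | Stop | Stop |
| Other grade 3-4 reaction not on the stop list | Interrupt, then 120 mg | Interrupt, then 80 mg | Interrupt, then stop* |

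*If the event is read as failure to tolerate 80 mg.

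The defect is confined to the first two rows of the 120 mg column. The two bullets in the 120 mg list name no starting dose, so read literally they still apply to a patient already on 120 mg. They return that patient to the same dose. Even a recurrent grade 2 hand-foot skin reaction at 120 mg leads to 80 mg.

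**Routes to a liver event at 120 mg.**
1. Recurrence after a liver event at 160 mg.
2. A first liver event after a reduction for another reason, such as hand-foot skin reaction.
3. A first liver event on the optional ramp in Section 4.1, which passes through 120 mg on days 8-14.

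**Whether other text closes the gap.**
- Section 4.5, after Table 4, says a lower regorafenib dose may be needed for regorafenib-related DLTs but names none. The only lower level in Table 7 is the excepted 80 mg.
- Section 4.6 ends treatment judged detrimental to health. That is discretion with no liver rule.
- Section 5.0 allows exceptions after discussion with the principal investigator. That is also discretion.
- Sections 5.2 and 5.3 set the entinostat and hydroxychloroquine doses, not the regorafenib dose.

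**Exposure only.** Inputs are the Note's upper figure of one third and the synopsis range of 32-44 patients: 32/3 = 10.7 and 44/3 = 14.7. Up to about 11 to 15 patients might need some decrease, and the first step is 120 mg. If the ramp is used, every patient on it who tolerates 80 mg also passes through 120 mg.

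**Background only.** Section 2.5 gives grade 3-4 bilirubin 7%, ALT 7% and AST 6% in the trial in Asia, without the overlap. The rate of any of the three lies between max(7, 7, 6) = 7% (full overlap) and 7 + 7 + 6 = 20% (no overlap). This is not a rate at 120 mg, and it includes events that already meet a stop criterion.

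**The case against.** The strongest reply is that the patient is not left unprotected or without an instruction. Interruption applies to every attributable grade 3-4 liver event. The two most worrying patterns are permanent stops. The 120 mg bullets supply a dose after recovery. All of that stands. A reader might infer from the exception that no post-recovery dose exists at all, but the documents do not support that reading. The fault is that the dose they give is unchanged, and so more lenient than for other reactions.

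A reader might also infer that every grade 3 or higher liver event at 120 mg is affected. That is too wide. AST/ALT above 20 x ULN is already a stop, so for transaminases the defect is grade 3 only. Grade 4 enters only through isolated bilirubin.

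The conflict between the Note and Section 5.0 is mild, because Section 5.0 allows exceptions and Section 4.1 describes early decreases followed by full doses as standard. Neither passage addresses liver events, however, so neither supports using the Note for them.

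Regorafenib is a marketed drug, and the text under Table 8 refers to the package insert. That pointer follows a toxicity table and brings in no dose rule. The insert is not among the documents, so it cannot be relied on to close the gap.

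Finally, the background range rests on one trial. The grade 3-4 toxicities listed for the other phase III trial in Section 2.5, and the rows of Table 8, include no liver abnormality. The 7% to 20% range therefore shows only that such events occur.

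**Conclusion.** Wrong as written, as a safety rule. At 120 mg, Section 5.1 manages the two residual kinds of liver event less strictly than other grade 3-4 reactions, and its AST/ALT bullet points to a Note that does not deal with the liver.

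This rests on three assumptions. The event is attributed to regorafenib. The undefined term hepatotoxicity covers isolated bilirubin elevation; if it does not, those events step down to 80 mg and the defect narrows to grade 3 AST/ALT. The bullets are applied as written.

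The number of affected patients cannot be estimated, because the documents give no rate of hepatotoxicity at 120 mg. Neither the 11 to 15 patients nor the 7% to 20% should be read as that number.

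Two stronger conclusions are tempting. One is that any liver event at 120 mg ought to be a permanent stop. The documents do not settle this for first events, and such a rule would be anomalous: the same first event at 160 mg only reduces the dose. The other is that the gap distorts the cycle 2 tolerability assessment in Section 4.3 or the response endpoint. Nothing in the documents quantifies such an effect, and none is claimed.

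**What to change.** Amend Section 5.1 in three places.

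1. Add to the permanent-discontinuation list: *recurrence of grade 3 or higher hepatotoxicity (AST, ALT or bilirubin) attributed to regorafenib despite reduction to 120 mg*.
2. For a first such event in a patient already on 120 mg, whether after a reduction for hand-foot skin reaction or on the Section 4.1 ramp, state the action: either 80 mg or a stop, at the sponsor's clinical choice, and not re-dosing at 120 mg or above. If 80 mg is chosen, reword the exception in the 80 mg bullet to match.
3. Delete the pointer to the Note from the AST/ALT bullet or replace it with liver-specific text, and state that the Note on returning to starting doses does not apply to hepatotoxicity.

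The cost is amendment wording. AST, ALT and total bilirubin are already in the scheduled chemistry panel (Appendix A, footnote 6). The downside is that a few patients, in a number that the documents do not allow to be estimated, may reduce or stop regorafenib earlier than they otherwise would.
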